### 2.2.1 Subgroup of interest

Since this study also includes pediatric patients, all key safety and efficacy analyses will be performed separately by age groups: 2-6 years (infant), 7-11 years (child), 12-17 years (adolescent), < 18 years (overall of infant, child and adolescent), and  $\geq$  18 years (adult). In addition, these summaries will be performed on prior intake of iron chelation status (naïve or pre-treated) and thalassemia transfusion status (TDT or NTDT).

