2.2 Rationale for the study design

This is an open-label, multicenter, single arm, phase II study which will enroll patients with transfusion-dependent thalassemia and non-transfusion-dependent thalassemia.

Patient preference is the primary objective of this study and will be addressed by measuring the proportion of patient claimed preference of deferasirox FCT over deferasirox DT assessed by a preference questionnaire at Week 48

Patients previously treated with iron chelators for at least 6 months continuously (excluding deferasirox) or who are chelator naïve will be eligible to participate in this study.

The study consists of two phases. The treatment duration for the core phase of 48 weeks is considered sufficient to assess the patient preference, safety, compliance and PRO profiles of the two formulations. Previous studies of pediatric and adolescent patients have demonstrated differences in iron chelation medication compliance within this time period ([Jordan 2012](#), [Alvarez 2009](#)). The extension phase permits patients to continue receiving deferasirox FCT for a maximum of 12 months after completion of the core phase, or until one of the end of study criterion is met, whichever comes first.

Patient preference for different ICTs, satisfaction, palatability and GI symptoms will be assessed via validated questionnaires; overall safety, efficacy of deferasirox (both DT and FCT) and pill count will be assessed as secondary objectives. The subgroups of interest are the patients with transfusion-dependent or non-transfusion-dependent thalassemia, as well as ethnicity.

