7.3.1 Preference Questionnaire

The preference questionnaire is a four item questionnaire. There are four separate versions depending on the week(s) that the questionnaire is administered.

For week 48 (primary endpoint) the first item asks the patients (or parents of young patients from 2 to 9 years old) which medicine they are currently taking with the response options: "Tablet to dissolve in liquid", "Film coated tablet ", "Sprinkle powder on food" and "I don't know". The second item asks which of the medicines did the patient "Like best" with the same response options as that of the first item. Finally, the third item asks the patient why he/she preferred the medicine they chose.

For week 28 the first item asks patients to choose from the following medicines: “Tablet to dissolve in liquid”, “Film coated tablet (taken once a day)”, “Tablet (taken 3 times a day)”, “Sprinkle powder on food”, “Injection” and “I don’t know”. The second items remain the same asking which medicine the patients like the best (out of the above response options). Similarly the third item remains the same.

For weeks 4 and 24 the first item asks patients to choose from the following medicines: “Tablet to dissolve in liquid”, “Tablet (taken 3 times a day)”, “Injection” and “I don’t know”. The second items remain the same asking which medicine the patients like the best (out of the above response options). Similarly the third item remains the same.

The following preference attributes are provided:

- Taste
- Aftertaste (taste left in your mouth after you swallow)
- Convenience (it’s not a problem to take your medicine - administration)
- Number of pills
- No/Less side effects
- Can correctly prepare the medicine
- Easier to remember to take the medicine
- Number of times you have to take the medicine
- No/Less pain on the injection site
- Gain my personal time with family and friends
- Other _____

The questionnaire is administered at week 4, week 24, week 28 and week 48. No total score is calculated on the preference questionnaire. Each item will be scored as the proportion of patients who select each response option.

7.3.2 mSICT – patients greater or equal to 10 years old

The Modified SICT (mSICT) questionnaire consists of 15 items that represent 3 domains; Adherence, Preference and Concerns.

The adherence domain consists of 7 items, 6 of which are measured using a 5 point response scale.

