10.5.2 Other secondary efficacy objectives

The following secondary analyses will be performed:

Patient preference of FCT, DT, and iron chelation at Week 28

Proportion and percentage, % (and 95% CI) of patients with preference and non-preference of FCT over DT, FCT over iron chelation, and DT over iron chelation will be summarized separately at Week 28.

Homogeneity test (Cochran's Q test) may be performed to check the homogeneity of the three preferences. Exact and asymptotic p-values of Mc Nemar's test will also be presented as analogous to primary analysis, for each pair of treatment comparison. For comparison of FCT

and DT with iron-chelation, only patients who are pre-treated with iron chelation will be selected.

Patient preference of DT and iron chelation at Week 4 and Week 24

Proportion and percentage, % (and 95% CI) of patients with preference and non-preference of DT over iron chelation will be summarized at Week 4 and Week 24. Exact and asymptotic p-values of Mc Nemar's test will also be presented as analogous to primary analysis. Only patients who are pre-treated with iron-chelation will be considered.

Reasons of patient preference

The reasons or factors influencing behind patient preference of FCT over DT will be summarized at Week 28 and 48. Proportions of patients for selecting each reason will be presented for each study treatment. Further summary of reasons behind non-preference of each study treatment will also be presented.

Compliance using pill count

Compliance is measured by pill /tablet count based on amount of medication dispensed, returned and reported as lost/wasted by the patient or caregiver. Compliance will be calculated for each treatment (FCT: Week 25- Week 48, DT: Baseline day 1 – Week 24) as the ratio of total count consumed to total count prescribed, where

total count consumed is derived from cumulative dispensed, returned and lost/wasted counts;

- total count prescribed is cumulative prescribed count

Analysis of covariance (ANCOVA) will be performed for comparison between both treatment groups (FCT and DT). The ANCOVA model for compliance endpoint will include treatment group and age group ((2 to <6 years, 6 to <10 years, 10 to <18 years, and ≥ 18 years) and thalassemia transfusion dependence (transfusion and non-transfusion dependent) as factors. Least squares estimates, 95% CI and p-value will be presented for each treatment and difference between treatments.

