## 2 Statistical methods

### 2.1 Data analysis general information

All analysis will be performed by NBS CONEXTS, Novartis.

It is planned that the data from all centers that participate in this study will be used for analysis. Analysis datasets and statistical outputs will be produced using the most recent SAS® Version 9.4 (SAS Institute Inc., Cary, NC, USA), and stored in Novartis global programming & statistical environment (GPS).

As the primary endpoint analysis will be performed at Week 48, there will be a database lock after all patients have completed Week 48 assessments. The proposed statistical analysis for interim analysis is described in [Section 2.14](#). A final database lock will occur when all patients have completed the study.

All summary statistics for continuous variables will include n (number), mean, standard deviation (SD), median, lower and upper quartiles (Q1, Q3), minimum, maximum, and, where applicable, the estimate and the 95% confidence intervals (CI) of mean. For categorical variables, descriptive statistics will include the number (frequencies) and percentage of patients in each category. Summary statistics will also be presented graphically wherever applicable.

If not otherwise specified, p-values and CI will be presented as two-sided. Unless otherwise stated, the default level of significance will be set to 5% (two-sided, family-wise type-I-error).

All data analysis will be presented by treatment group, i.e. DFX DT and DFX FCT, iron chelation status (naïve or pre-treated) and by thalassemia transfusion status (TDT or NTDT), wherever applicable. Efficacy and safety data for the core and extension phases will also be presented by the above groups. Since this study also includes pediatric patients, all key safety and efficacy endpoints will also be summarized by the age groups as defined in the protocol and [Section 2.2.1](#).

The analysis will be conducted on all patients' data at the specific time-points (Week 4, 24, 28, and 48), wherever applicable and at the time the study (both core and extension phases) ends.

Unless otherwise specified, if there are additional data available for any assessment (for example data on unscheduled visit) then the average of the available values will be presented under the dedicated visit.

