**Compliance using pill count**

Compliance is measured by pill/tablet count based on amount of medication dispensed, returned and reported as lost/wasted by the patient or caregiver. Compliance will be calculated for each treatment (FCT: Week 25- Week 48, DT: Baseline day 1 – Week 24) as the ratio of total count consumed to total count prescribed, where total count consumed is derived from cumulative dispensed, returned and lost/wasted counts and total count prescribed is the cumulative prescribed count.

The prescribed count corresponds to the count prescribed by the investigator for a period that the patient should have taken during this period. For each strength (125 mg, 250 mg and 500 mg tablets for Deferasirox DT; 90 mg, 180 mg and 360 mg tablets for Deferasirox FCT), the prescribed count for a period is calculated from the daily prescribed count at the beginning of this period multiplied by the duration (days) of this period. The daily prescribed count is the sum of counts prescribed per strength. The duration of a period will be calculated as (end date of the period) – (start date of the period) + 1. The following period duration calculation will exclude the start day. The total count prescribed is the sum of counts prescribed over all periods.

If a patient does not return the study drug, the compliance will not be calculated.

Analysis of covariance (ANCOVA) will be performed for comparison between both treatment groups (FCT and DT). The ANCOVA model for compliance endpoint will include treatment group and age group (2 to < 6 years, 6 to < 10 years, 10 to < 18 years, and  $\geq$  18 years) and thalassemia transfusion dependence (TDT and NTDT) as factors. Least squares estimates, 95% CI and p-value will be presented for each treatment and difference between treatments.

Summary statistics of number of pills (and percentages) will also be presented overall and by treatment and subgroups.

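### The SAP's age bands are not the protocol's, and the 7–11 and under-18 rows of the supportive Week 48 preference analysis mix parent and patient answers

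*SAP*

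**What the plan says.** SAP 2.1 states that "all key safety and efficacy endpoints will also be summarized by the age groups as defined in the protocol and" its own Section 2.2.1. Section 2.2.1 then says "all key safety and efficacy analyses will be performed separately by age groups: 2-6 years (infant), 7-11 years (child), 12-17 years (adolescent"), followed by under-18 and adult groups. SAP 2.3.2 uses the same bands for demographics, and SAP 2.5.4 uses them for the primary preference analysis by age. SAP 2.5.4 also says that subgroup analyses carry no p-values.

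The protocol gives analysis age bands in one place, the compliance ANCOVA in section 10.5.2: "2 to <6 years, 6 to <10 years, 10 to <18 years, and" ≥18 years. SAP 2.7.2 keeps that factor for its own compliance model: "age group (2 to < 6 years, 6 to < 10 years, 10 to < 18 years, and" ≥18. SAP Section 4, on changes to protocol-specified analyses, is marked not applicable.

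On who answers, Protocol 7.3.1 says of the Week 48 form that "the first item asks the patients (or parents of young patients from 2 to 9 years old) which medicine they are currently taking". Footnote 8 of Protocol Table 7-1 gives the same 2–9 range for observer reports across the PROs. SAP 2.11 summarises palatability and mSICT separately for self-reporting and observer-reported patients. For preference it refers back to SAP 2.5 and 2.7 and states no such split.

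**The concern.** There are two linked problems. First, a reader who follows the pointer in SAP 2.1 to the protocol finds different bands, and the SAP itself carries both schemes without saying so. Second, the scheme chosen for the preference analysis cuts across the age at which the respondent changes. A parent's view of which formulation a seven-year-old likes best is a different measurement from an eleven-year-old's own answer. In a row that holds both, the percentage depends partly on how many of each were recruited. The SAP guards against this for two secondary questionnaires but not for the endpoint on which the trial is judged. At stake is how the 7–11 and under-18 rows can be interpreted, in a study that enrols from age 2.

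**Working it through.** **Design figures.** The plan gives no number for this point, so there is none to reproduce. Its sample size shows that age does not enter the primary test. With 45% preferring FCT and 25% preferring DT, the discordant share is 0.70 and the difference 0.20. McNemar's test with the variance under the alternative gives n = (1.960 + 0.842)² × (0.70 − 0.20²) / 0.20² = 129.5, so 130. Then 130 / 0.9 = 144.4, so 145. Both match Protocol 10.8 and SAP Section 3, and neither depends on age bands.

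**Age by age.** Each year of age is placed in its band under both schemes, with the respondent from Protocol 7.3.1.

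| Age | SAP 2.5.4 band | Protocol 10.5.2 band | Respondent |
|---|---|---|---|
| 2–5 | 2–6 | 2 to <6 | parent |
| 6 | 2–6 | 6 to <10 | parent |
| 7–9 | 7–11 | 6 to <10 | parent |
| 10–11 | 7–11 | 10 to <18 | patient |
| 12–17 | 12–17 | 10 to <18 | patient |
| ≥18 | ≥18 | ≥18 | patient |

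- SAP bands: 7–11 holds three parent-answered years (7, 8, 9) and two self-answered years (10, 11). The under-18 row holds eight of each (2–9 and 10–17). The other three rows have one kind of respondent.
- Protocol bands: no band mixes respondents, because they break at 10.
- Ages 6, 10 and 11 fall in non-corresponding bands under the two schemes.

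**Possible size.** The documents give neither preference by respondent nor an age distribution, so every rate here is assumed. If the parent share of a row is w, the row shows w × (parent rate) + (1 − w) × (patient rate).

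| Assumed parent / patient rate | w = 0.2 | 0.4 | 0.6 | 0.8 |
|---|---|---|---|---|
| 45% / 45% | 45% | 45% | 45% | 45% |
| 60% / 30% | 36% | 42% | 48% | 54% |
| 30% / 60% | 54% | 48% | 42% | 36% |

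Ages spread evenly over 7–11 would give w = 3/5 = 0.6. The movement equals the change in parent share times the gap between respondents: 0.6 × 30 = 18 points in the lower two lines, and zero if the respondents agree. For scale, the design difference is 20 points.

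**The case against.** The case against giving this much weight is strong on scope.

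- **The protocol has no age subgroups to depart from.** Its bands are only a model factor. Protocol 2.2 says "The subgroups of interest are the patients with transfusion-dependent or non-transfusion-dependent thalassemia, as well as ethnicity". Protocol 10.4.4 lists supportive analyses by transfusion dependence, prior chelation and switching, not age. SAP 2.1 also points to its own Section 2.2.1, where the operative bands are clear. This stands: the fault is a reference to a definition that does not exist for this purpose, not the replacement of one that did. The reference is still wrong.
- **The rows are supportive and descriptive.** Only one of the four distinct bands mixes respondents, and no p-values are attached. This stands. A reader might infer that the primary result, or the whole by-age display, cannot be interpreted. The documents do not support that, since the primary test uses all eligible patients regardless of band and three of the five rows are homogeneous.
- **Changing the bands does not separate age from respondent.** Respondent is set by age, so any comparison across age 10 still confounds the two. This stands. The gain is only that each narrow row has one known kind of respondent.
- **Two schemes need not mean conflicting tables.** The compliance model is specified to report estimates for each treatment and their difference, not by age. This stands. A reader might expect the same child to appear in different age rows of different tables, but no output showing the model's age bands is specified.
- **The size is assumed.** This stands, and the gap could be zero.

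None of this removes the mixed 7–11 row or supplies a respondent split for preference.

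**Conclusion.** The point holds in a limited form. The SAP attributes its age groups to the protocol, uses different ones and declares no change. As a result, the 7–11 and under-18 rows of the supportive Week 48 preference analysis combine parent and patient answers. The primary McNemar test, its alpha and the 130/145 sample size are untouched. The possible distortion depends on an unknown gap between respondents. It is nil with no gap, and an 18-point swing in the 7–11 row under an assumed 30-point gap with parent shares from 20% to 80%.

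The conclusion rests on the 2–9 parent rule being applied as written. I found no statement of whether age is fixed at enrolment or taken at each visit. A child who turns 10 during the 48 weeks could therefore change respondent. This is a cheap improvement, not a threat to the trial's main conclusion.

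**What to change.** 1. In SAP 2.5.4, present Week 48 preference in age rows that break at 10. The protocol's bands do this, and the 12-year cut can stay as an extra row. Alternatively, or as well, add a parent-answered (2–9) versus self-answered (≥10) pair of rows, following what SAP 2.11 does for palatability and mSICT. The pair also shows what lies inside the under-18 row.
2. State whether age is taken at enrolment or at the visit, for both the bands and the choice of respondent.
3. In SAP 2.1, correct the wording "will also be summarized by the age groups as defined in the protocol", and record the difference in SAP Section 4.
4. Label any rows added now as defined after the interim lock. The SAP history dates the latest entries 08-Apr-2021 and marks that day's addendum as after that lock, and SAP 2.14 places the primary analysis at the interim.

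The cost is a few extra descriptive rows and some SAP wording. The safety and demographic tables can keep their present bands. With this change each narrow preference row has one kind of respondent, but an age effect still cannot be told from a respondent effect, and the text accompanying the table should say so.

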## **2.3 Patient disposition, demographics and other baseline characteristics**

Descriptive statistics will be provided for patient disposition, demographics and all baseline characteristics including baseline values of main efficacy endpoints.

Summary statistics will be presented for continuous variables of the subgroup of interest and for all patients in the Enrolled Set. The number and percentage of patients in each category will be presented for categorical variables for the subgroup of interest and all patients.

Patients with missing data will not be included in the calculation of the percentages.

### **2.3.1 Patient disposition**

The Enrolled Set will be used for the summary and listing of patient disposition. The overall number and percentage of patients who were screened, completed (core phase, extension phase) and discontinued the study (core phase or extension phase) along with reasons for discontinuation will be summarized.

### **2.3.2 Patient demographics**

Summary statistics will be presented for continuous demographic variables by the subgroup of interest and for all patients in the Enrolled Set. For categorical variables, number and percentage of patients in each category will be presented for subgroup of interest and all patients.

The following demographic variables will be summarized:

Continuous variables:

- Age (years)
- Height (meter)
- Weight (kg)
- Body mass index (BMI) = (body weight in kilograms) / (height in meters)

For BMI, height and body weight used is the last value prior to randomization. If there is no weight recorded prior to taking of study drug, BMI will be missing.

Categorical variables

- Age group ( 2 years ≤ age < 7 years, 7 years ≤ age < 12years, 12 years ≤ age < 18 years, < 18 years (overall of infant, child and adolescent), and age ≥ 18 years)
- Gender (male, female)
- Ethnicity (Hispanic/Latino, Chinese, Indian (Indian subcontinent), Japanese, Other)

### **2.3.3 Patient baseline characteristics**

Summary statistics will be presented for continuous baseline variables by subgroup of interest and for all patients in the Enrolled set. For categorical variables, number and percentage of patients in each category will be presented for subgroup of interest and all patients. Baseline characteristics will be summarized depending on the following histories and tests:

- Disease history
- Prior chelation therapy
- Transfusion history

Baseline disease characteristics will be summarized for the following variables:

- Disease history continuous variables
  - Time since diagnosis (months)
- Disease history categorical variables
  - Disease type (Transfusion-dependent thalassemia, Non-transfusion-dependent thalassemia)
  - Patients who are hematologically stable since the examination (Yes/ No)
- Prior chelation therapy continuous variables
  - Time since last iron chelation therapy (from end date)
  - Duration of last iron therapy (days)
  - Average daily dose (DFO) (mg/kg)
  - Average daily dose (DFP) (mg/kg)
  - Average daily dose of DFO or DFP (mg/ kg)
  - Average daily dose 1 (Other) (mg/kg)
  - Average daily dose 2 (Other) (mg/kg)
- Prior chelation therapy categorical variables
  - Patients who have received a chelation therapy in at least last 6 months prior to start of study drug (Yes/ No), where ‘Yes’ means prior chelation treated and ‘No’ means prior chelation naïve.
  - Medication name (DFO, DFP, DFO and DFP, Other)
- Transfusion history continuous variable
  - Total number of transfusion(s) received in last 12 months (units)
  - Time since last transfusion received (days)
  - Number of units last transfused
    - Platelets
    - PRBC
    - White blood
- Transfusion history categorical variable
  - The subject received blood transfusion prior to study (Yes/ No)

### Medical history

Relevant medical history and current medical conditions will be summarized by system organ class and preferred term of the MedDRA dictionary. Other relevant baseline information will be listed and summarized using descriptive statistics, as appropriate.

## 2.4 Treatments (study treatment, rescue medication, concomitant therapies, compliance)

### 2.4.1 Study treatment / compliance

#### Study treatment

The following variables will be summarized descriptively for each study treatment period based on the Safety Set. Summaries will be presented overall and by age groups and also on prior intake of iron chelation status (naïve or pre-treated) and thalassemia transfusion status (transfusion or non-transfusion), separately for Core and Extension phases.

- The number of medications (pills) received for each dosing regimen
- The duration of exposure (in weeks) and in categories (< 4 weeks, 4-< 12 weeks, 12-< 24 weeks, ≥ 24 weeks)
- Average planned (mg/kg/day) and average actual daily dose (mg/kg/day)
- Cumulative planned (mg/kg) and cumulative total actual dose (mg/kg)
- Percentage of planned dose taken
- Dose intensity (computed as the ratio of actual cumulative dose received and actual duration of exposure)
- Relative dose intensity (computed as the ratio of dose intensity and planned dose intensity)

The number of patients with dose adjustments (increase, reductions, interruption, or permanent discontinuation) and the reasons of change and interruption will be summarized for all patients and by treatment group. Dose adjustments for auditory, hypersensitivity reactions and cytopenias will also be summarized.

The number of patients with ‘switching’ (this is a switch outside the normal switch at the end of Week 24) from one treatment to another at any treatment period along with the reasons of switching will also be summarized. In case of switching within each treatment period, duration of exposure will be calculated accordingly as described below.

The duration of exposure is defined as the number of weeks between the start and end of study medication. The exposure calculation will be based on the actual date of switch from one treatment to another. The end of study medication day is the last day with a non-zero actual dose of study medication as recorded on the drug administration pages.

The average daily dose (planned or actual, in mg/kg) is calculated as the mean dose over all days between first and last dose, including interim days with zero dose (interruptions). The final daily dose is recorded as the last non-zero dose. The cumulative dose is calculated as the sum over the daily doses of all days between first and last dose. The current weight is used when calculating the actual daily dose.

The percentage of planned dose taken is derived as  $100 * \text{cumulative actual dose (mg/kg)} / \text{cumulative planned dose (mg/kg)}$ .

